### C. PRELIMINARY STUDIES

**Pilot naturalistic study:** 47 youth with a BMI > 85%ile and prescribed an SGA were treated with MET at CCHMC's residential treatment facility, using a MET dose titrated to 850 mg 2x/day over 2-4 weeks, with a further increase to 1000 mg 2x/day by 2 months if weight gain continued. BMI z score was the primary outcome measure. Electronic medical record data from two groups of these MET-treated patients were analyzed (MS submitted for publication): Group 1 (SGA non-naïve) was taking SGAs for at least 2 months (mean  $\pm$  SD = 9.2  $\pm$  7.2 months, range= 2.3 - 24.9) prior to MET initiation (n=29, 47% girls, age=13.9 years  $\pm$  2.5); Group 2 (SGA naïve) started on MET and SGAs simultaneously (n=18; 59% girls, age=14.2 years  $\pm$  2.8). The groups were similar, and, as in our previous report, 40% received > 1 psychotropic medications. 80% of the SGA non-naïve patients had weight gain > 7% over the 2 months prior to MET initiation and exhibited a 0.45 sd increase in their BMI z score (Figure 1). Surprisingly, more of the SGA naïve (94%) than the SGA non-naïve (78%) patients had a BMI > 95%ile at MET initiation. BMI Z score was stabilized by MET in both groups, but there was a significant group by month interaction ( $p=0.003$ , generalized linear model), even after controlling for the higher baseline BMI z score ( $p=0.002$ ).

**Figure 1: MET prevention and intervention effects SGA-induced weight gain in youth**  
**Group1=SGA-non-naïve Group 2= SGA-naïve**

This group difference resulted in part from the immediate decrease in BMI z score in the SGA naïve group (BMI z score decreased by 0.23). BMI z score of the SGA non- naïve group decreased by 0.27+0.5 during the 6 months on MET. SGA naïve patients responded at lower MET doses than SGA non-naïve patients ( $764 \pm 225$  mg/d vs.  $834 \pm 285$ ). Additional determinates of MET response were: 1) Higher baseline BMI z score ( $p<0.0001$ ); 2) Longer length of SGA treatment prior to MET initiation ( $p=0.049$ ); and, 3) A  $> 7\%$  increase in weight over the 2 months prior to starting MET ( $p=0.0007$ ). These data confirm our previous results that MET abrogates SGA-induced abnormal weight gain in youth and also adds concerning information that a larger proportion of youth on SGAs are affected by weight gain than previously reported.

**IMPACT Study:** Most recently, [name] completed a large rigorously controlled NIMH-supported study of youth with psychiatric disorders and  $\text{BMI} > 85\%$ ile and SGA-related weight gain. Participants were randomized to 1 of 3 arms: 1) continuation of current SGA (control arm) ( $N=44$ ); 2) switch from current SGA to lower-risk agent (LRA) ( $N=30$ ) or 3) co-treatment with MET + continuation of current SGA (MET) ( $N=46$ ).

Sample characteristics were as follows: Age: 13.7 (7.6-19.9;  $<18=88\%$ ) Male=65% Hispanic:12% Black: 28%. At 12 and 24 weeks there was a significant decrease in BMI Z-scores in the MET (-0.034, -0.088, respectively) and LRA (-0.051, -0.112) groups compared with the control group (+0.026, +0.040). Additionally, at 24 months weight gain in the control group was 8.5lbs and 0.3lbs in the LRA group. In contrast, the MET group had an average decrease of -0.4lbs. 14.9% in the MET lost  $>5\%$  of weight compared to 2.3% in the control group and 10.0% in the LRA group (Fisher's exact,  $p=0.059$ ). Importantly, dropout rates in the LRA (39%) and control (28%) groups were higher than in the MET (24%) group. The most common (58%) reason for discontinuation in the LRA group was "inadequate therapeutic effect."

These findings confirm those of prior studies, including our own. However, these, along with previous studies, have been conducted in academic settings, typically with many rigorous study criteria. Findings from such studies may not be generalizable to BSD youth treated in community settings where access to these interventions (e.g. healthy lifestyle strategies and medications) is often limited. Moreover, patient-centered outcomes were not assessed in these studies.

## **E. EXPERIMENTAL DESIGN & METHODS**

### **a. Methods and Procedures**

**Study Overview:** We propose a prospective, large, PRAGMATIC, randomized trial to study the impact of MET and healthy lifestyle intervention (LIFE) vs. LIFE alone on patient-centered outcomes of body weight, SGA-adherence and satisfaction, psychiatric symptom burden (e.g. mood/anxiety), and QoL. We will also examine metabolic outcomes.

The focus of the pragmatic trial is to determine which intervention is most effective through observation of care as usual conditions or in “real-world clinical settings” rather than under controlled experimental circumstances. Information should be collected when available as part of routine clinical practice rather than through study-specific procedures, with minimal interference to clinical practice. Adherence to protocol recommendations from practitioners and patients are observed and documented throughout the study.

**Subjects:** We propose to recruit approximately 1800 overweight/obese youth with BSD who are prescribed SGAs from at least 40 public and private mental health practices (approximately 900 each from sites under the coordination of University of Cincinnati, Midwestern center and from within the sites under the Northwell Health East Coast coordinating center), to participate in the proposed patient-centered large pragmatic trial examining the effectiveness of MET and LIFE vs. LIFE alone. Patients will be eligible for study participation if they are:

1. Inpatient or outpatient age 8-19 years inclusive; participants must live with a parent, guardian, or caregiver;
2. Fluent in English;
3. Diagnosed or told by a clinician that they have any of the following bipolar spectrum disorders (BSD): bipolar I, bipolar II, unspecified bipolar and related disorders, Disruptive Mood Dysregulation Disorder (DMDD), cyclothymic disorder, other specified bipolar and related disorders, as well as mood disorder not otherwise specified (if diagnosed in the past as per DSM-IV);
4. Body mass index  $\geq 85\text{th}$  percentile for age and sex by standard growth charts;
5. Received a new or ongoing prescription for at least one SGA (i.e., olanzapine, clozapine, risperidone, quetiapine, aripiprazole, ziprasidone, iloperidone, lurasidone, paliperidone, brexpiprazole or cariprazine) that is not prescribed as a PRN medication

Additionally, patients will be excluded by the following:

1. Patients will be excluded if they have had exposure to a total daily dose of MET 1000 mg bid for at least 2 weeks in the past 3 months;
2. Patients will be excluded if they could not tolerate MET during the recommended titration schedule outlined in the protocol;
3. Major neurological or medical illnesses that affect weight gain (e.g., unstable thyroid disease) or require a systemic medication that might impact weight or glucose regulation (e.g., diabetes mellitus [insulin], chronic renal failure [steroids]);
4. If lab results are available in the last 6 months, then a fasting serum glucose  $\geq 126 \text{ mg/dL}$  on two occasions prior to or during screening, indicating need for prompt treatment.
5. If lab results are available in the last 6 months, then a serum creatinine  $\geq 1.3 \text{ mg/dL}$  on two occasions during screening and/or follow-up, indicating potential impairment of renal functioning
6. Pregnant or breast feeding;
7. Based on their clinician's assessment, children and caregivers who are unable to complete screening/baseline assessments for any reason;

The enrollment rate will be approximately 1-2 patients/month/site for a recruitment time of 57 months.

**Randomization:** We will randomize 1800 patients (1:1 ratio) to either MET + LIFE or LIFE alone. All patients will receive a lifestyle intervention (LIFE) of brief standardized education. Once a patient is determined to meet the above criteria and has provided appropriate informed consent/assent, site staff will assign the participant a patient ID number. The site staff will then log on to the study's REDCap site and enter the Patient ID, and the following stratification factors: site, overweight or obese, previous SGA exposure, and sex of patient (transgendered patients will be randomized according to sex assigned at birth). REDCap has a built in mechanism that prevents duplication of subject ID numbers.

Once all stratification factors have been entered, the REDCap randomization module will return the next assignment for the appropriate strata.

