## **OUTCOME MEASURES:**

Due to MOBILITY being a pragmatic and largely observational study, any participant who is deemed eligible by the above criteria will be enrolled in MOBILITY. These criteria, along with providing appropriate informed consent/assent, are the necessary criteria for participation in MOBILITY. We will continue to collect data in a naturalistic manner from all patients who have met these criteria regardless of whether they begin the intervention to which they have been randomized or have not attended all of their clinical follow up appointments. Patients will have follow-up study visits and data collected concurrent with their existing CLINICAL visit schedule.

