Screening laboratory tests recommended include renal and hepatic function tests, electrolytes, CBC and thyroid stimulating hormone (TSH), as per Table 2. However, we will collect any results of labs performed within the last six months, if available. The only mandatory test for screening will be a pregnancy test in girls of menarche.

Every attempt will be made to encourage clinicians to obtain laboratory testing prior to starting metformin, however, patients who have not had baseline labs will continue to be followed in MOBILITY.

Kiddie-SADS-Present and Lifetime (K-SADS-PL 2013): After discussion with our patient/parent partners and site clinicians, we determined that the appropriate study population is all patients who receive a clinical diagnosis of a BSD, as these patients will typically receive SGA treatment regardless of whether they meet full DSM criteria. However, it was decided that using a structured research interview would provide an opportunity to examine concordance of clinical and research diagnoses and to assess HTE (i.e., do youth with a research diagnosis respond to MET differently than those with only a clinical diagnosis because risk for overweight/obesity and metabolic disorder may be higher for those with a research BSD diagnosis). Therefore, BSD diagnoses will be confirmed with the mood modules of the K-SADS-PL, a semi-structured diagnostic interview with established test-retest reliability. (Interviewers will be trained by qualified personnel. Trained staff at the respective coordinating centers who are not associated with the clinical sites will administer the interview separately to guardians and patients, if > 12 years old). Based on feedback from the clinical sites, we determined that having their staff administer the K-SADS-PL might create diagnostic confusion, therefore, we will develop a mechanism that clinicians will be provided with the K-SADS-PL diagnoses after participants have reached Month 6 of study participation.

Table 1. Metformin (MET) Titration		
	<50kg AM/PM	≥50kg AM/PM
Week 1	0/500mg	0/500mg
Week 2	0/500mg	0/500mg
Week 3	500/500mg	500/500mg
Week 4	500/500mg	500/500mg
Week 5	500/1000mg	500/1000mg
Week 6	500/1000mg	500/1000mg
Week 7	500/1000mg	1000/1000mg
Week 8	500/1000mg	1000/1000mg

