Participants randomized to treatment with MET will start at a recommended dose of 500 mg orally at night and slowly titrated in 2-week intervals to ensure that each patient achieves maximum insulin-sensitizing effects of the drug while minimizing the chance of side effects (see Table 1). We selected 50kg as the weight at which we felt comfortable increasing to a maximum total daily dose of 2000mg (1000mg twice daily). These youth will be at a low-end adult-comparable weight. We anticipate that most participants  $\geq$ 10 years old will be  $>50$ kg, which is the 95%ile for weight for 10-year-olds of both sexes. Children  $<50$ kg, likely those patients  $<10$  years, will have a reduced maximum daily dose of 1500mg. If

patients exhibit untoward gastrointestinal side effects while taking MET, clinicians will have the option to switch to an equivalent dose of the once-daily extended-release form of MET, which may alleviate side effects. If a patient does not tolerate a specific dose, the clinician will also have the option of reducing that dose by 500mg/day to a minimum recommended daily dose of 500mg twice daily. At Week 8, the dose for the <50kg group may be titrated to the maximum of 2000mg/day (1000mg twice daily) if tolerated and strategy, in general, MET will be at steady-state target levels well before key outcomes are assessed at Month 6. We will also recommend that MET be taken with food to minimize side effects. If a participant's BMI percentile <5% (=underweight) his/her treatment with MET will be discontinued. Although the risk of low vitamin B12 while taking MET is associated with age > 50 years and having type II diabetes, we will monitor B12 levels and a CBC throughout study participation.

Clinicians and patients must be willing to be randomized to either treatment arm. However, the clinician may choose to initiate or continue (for those on a subtherapeutic dose) metformin at their clinical discretion regardless of randomization following a recommended initial 3 month period of treatment. These patients' data will be considered in a different analytic group regardless of randomization.

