**Other potential risks:** To guard against frustration and fatigue, questions and surveys have been carefully chosen by patients, parents, and stakeholders. However, when necessary, assessments can be divided to decrease the frustration and fatigue. In addition, research staff will be hired based on their research experience and work with children and adolescents. Lastly, patients and their parent(s)/legal guardian(s) will be advised that they do not have to participate in the study and that their participation is voluntary and refusal to participate will not impact their clinical care in any way. Their alternative to study participation is to continue to receive standard clinical care. **Additional weight gain or metabolic abnormalities:** Patients in the study will be closely monitored for weight gain and metabolic abnormalities. Clinicians, parents, or patients can discontinue assigned study treatment at any point, but will still be monitored for up to 24 month. If a patient continues to have substantial weight gain ( $> 10\%$ ) in the LIFE group, a clinician might decide to add MET to the treatment if clinically indicated. Likewise, if the patient is randomized to the MET + LIFE group and continues to have substantial weight ( $> 10\%$ ) they will have the option to continue MET and/or add another treatment or switch the patient's treatment for BSD, whichever is clinically indicated. If a participant's BMI percentile 5% (= underweight) his/her treatment with MET will be discontinued.

Although the risk of low vitamin B12 while taking MET is associated with age  $> 50$  years and having type II diabetes, we will encourage clinicians to monitor B12 levels and a CBC throughout study participation. We will educate all study-related clinicians about this potential side effect of metformin and the very rare clinical manifestations of MET-related vitamin B12 deficiency (i.e., peripheral neuropathy and pernicious anemia).

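### Moving patients who start or continue metformin into a separate analytic group would undo randomisation for the BMI z-score comparison; they should be analysed as randomised

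*Combined protocol and SAP*

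**What the plan says.** Exclusion 1, given in Section E.a and repeated in Section F.c, removes patients with "exposure to a total daily dose of MET 1000 mg bid for at least 2 weeks in the past 3 months". The start of Outcome Measures makes the listed criteria operative: "any participant who is deemed eligible by the above criteria will be enrolled in MOBILITY". Intended Demographics (Section F.d) describes the exclusion more loosely, as current or earlier therapeutic metformin exposure, with no dose, duration or look-back.

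The dosing text after Table 2 foresees entrants already on metformin. After a recommended first three months, a clinician may "initiate or continue (for those on a subtherapeutic dose) metformin at their clinical discretion regardless of randomization following a recommended initial 3 month period". The next sentence says that these patients' "data will be considered in a different analytic group regardless of randomization". Section G.a adds that after weight gain above 10% "in the LIFE group, a clinician might decide to add MET to the treatment if clinically indicated".

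The analysis text in Section E.b points the other way. Its basic model has change from baseline to 6 or 24 months as outcome, with randomised group, baseline value and random site effects as terms. It does not mention a separate group for metformin starters or continuers. It plans no analysis restricted to patients not on metformin at baseline.

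**The concern.** Randomisation makes the two arms comparable only while patients are compared by the arm they were assigned. A group defined by who later starts or continues metformin is formed by decisions taken after assignment. In the LIFE arm, one stated reason for such a decision is weight gain, which is closely tied to the primary outcome. If those patients leave the arm comparison, the LIFE arm loses some of its worst outcomes with no matching loss from the MET arm. The estimate then mixes the effect of metformin with the effect of the selection.

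The two passages also cannot both govern the primary analysis. An analyst who follows the dosing text and one who follows Section E.b would analyse different patients at 6 and 24 months. The documents do not say which text prevails.

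**Working it through.** **1. Who can enter on metformin.** Exclusion 1: 2 × 1000 = 2000 mg/day. The schedule headed "Table 1. Metformin (MET) Titration" ends at 500 + 1000 = 1500 mg/day under 50 kg and 1000 + 1000 = 2000 mg/day at 50 kg or more. The lowest recommended dose is 2 × 500 = 1000 mg/day. So a patient on less than 2000 mg/day, on 2000 mg/day for under two weeks, or on it only more than three months ago is eligible under the numbered criteria. The reference to a subtherapeutic dose shows that lower-dose users are expected.

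**2. The rules side by side.**
- Dosing text: starters and continuers go to another analytic group, whatever their assignment.
- Section G.a: in the LIFE arm, weight gain above 10% can be the reason for starting.
- Section E.b: the model term is the randomised group.
- Specific Aims, H1.1: the hypothesis concerns assignment to metformin.
- Outcome Measures and Section G.b: data are collected whether or not the assigned treatment is started or later switched.

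The last three fit an as-randomised analysis, and the data for it will exist. The first does not fit, and with the second it selects on the outcome. The three-month recommendation does not protect the 6-month endpoint, because discretionary starts can fall between months 3 and 6. The marginal structural weights in Section E.b model changes in SGA regimen; no weighting for starting metformin is described.

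**3. Illustration of the selection.** Section F.b gives no power derivation, so there is no planned effect or SD to reproduce. Inputs from Section C:
- Difference at 24 weeks in the prior three-arm trial: 0.040 − (−0.088) = 0.128 z.
- SD of change: 0.5, reading the pilot's 0.27+0.5 as mean ± SD.

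Assumptions not in the documents: a share q of the LIFE arm is moved out because a normally distributed weight trigger exceeds its cut-off, and the trigger correlates ρ with BMI z change. The LIFE mean then falls by ρ × SD × φ(z) / (1 − q), where z is the upper-q normal point.

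| q | φ(z)/(1 − q) | Fall, ρ = 0.25 | Fall, ρ = 0.5 |
|---|---|---|---|
| 5% | 0.1031/0.95 = 0.109 | 0.014 | 0.027 |
| 10% | 0.1755/0.90 = 0.195 | 0.024 | 0.049 |
| 20% | 0.2800/0.80 = 0.350 | 0.044 | 0.087 |

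The observed difference would be 0.128 minus the fall: between 0.114 and 0.041. With 90% retention (Section F.f), 900 × 0.9 = 810 per arm, and the 95% CI half-width is 1.96 × 0.5 × √(2/810) = 0.049. Here the bias runs against metformin. Moving out LIFE-arm patients who continued a baseline dose and gained little would push the other way, so the net direction is not fixed.

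**4. If everyone is analysed as randomised.** Let p be the share on metformin at baseline (assumed) and r their between-arm difference relative to other patients. The overall difference is 0.128 × (1 − p(1 − r)). For p = 5%, 10%, 20%:
- r = 0: 0.122, 0.115, 0.102.
- r = 0.5: 0.125, 0.122, 0.115.
- r = 1.5, as when LIFE-arm users stop and regain: 0.131, 0.134, 0.141.

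This is a valid effect of assignment in the patients enrolled. The arithmetic applies only if the dosing-text rule is not used.

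**5. The optional sensitivity analysis.** In patients not on metformin at baseline the half-width grows by 1/√(1 − p):
- p = 5%: 0.050, about 3% wider.
- p = 10%: 0.051, about 5% wider.
- p = 20%: 0.054, about 12% wider.

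At p = 20% and r = 0 (two-sided 5%, normal approximation), power for the full sample against this subset is 0.985 against 0.996 at SD 0.5, and 0.785 against 0.867 at an assumed SD of 0.75. Any statement that power is unaffected therefore holds only near SD 0.5. Site effects and baseline adjustment are ignored throughout.

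**The case against.** The strongest reply is that the trial is deliberately pragmatic, that Section E.b already models by randomised group, and that the dosing-text sentence may mean only an extra analysis. Clinicians and patients must also accept either assignment, and discretionary metformin is meant to wait three months. This stands in part: a reader might infer that the primary analysis is definitely as-treated, and the documents do not support that. They contain two incompatible statements and no rule of precedence. The three-month wait is only recommended and ends before the first primary time point.

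A reader might also infer that exclusion 1 is set at the wrong dose, because a child under 50 kg "will have a reduced maximum daily dose of 1500mg" and could enter already taking it. That does not hold as an error. The same text says that at Week 8 "the dose for the <50kg group may be titrated to the maximum of 2000mg/day", so 2000 mg/day is the eventual maximum in both weight bands, and lower-dose users are admitted by design. A 1500 mg/day cut-off for lighter children is a preference.

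Nor does Section F.d set a competing eligibility rule. The numbered criteria are operative, and therapeutic there may be shorthand for exclusion 1. The missing look-back is a wording gap. Finally, baseline users do not invalidate an as-randomised comparison, and the documents do not show that they threaten its power.

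**Conclusion.** The point holds in a narrow form. If the separate-group rule is applied to the primary analysis, patients leave the arm comparison for reasons that can include the outcome, and the BMI z-score estimate is biased. The rule also conflicts with the model in Section E.b. If Section E.b governs, the comparison is sound and only the conflicting sentence needs correcting.

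The size is unknown. The documents give neither the share on metformin at baseline nor the share who will start it later. The 0.014 to 0.087 z range rests on assumed shares of 5% to 20%, assumed correlations of 0.25 and 0.5, a normal trigger, and an SD of 0.5 taken from a small uncontrolled pilot group. It shows that the selection could matter next to 0.128 z; it does not predict that it will. The point is minor in the work needed to correct it.

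**What to change.** 1. Amend the dosing text after Table 2, and say the same in Section E.b: in the 6- and 24-month primary analyses every patient is analysed in the arm randomised, whatever metformin is started, continued or stopped. The group of starters and continuers is reported descriptively only. This costs a few sentences and no data.

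2. Optionally, flag metformin use at randomisation from the baseline medication list in Table 2, and prespecify an as-randomised sensitivity analysis of BMI z-score change in patients not on metformin at baseline. That subset is fixed before assignment, so the comparison stays randomised. It costs one extra model and a CI about 3% to 12% wider than the full sample at an assumed 5% to 20% baseline use.

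3. As an editorial clarification, write exclusion 1 as 2000 mg/day, since joining total daily dose to a twice-daily dose could be misread as 1000 mg/day. Give Section F.d the same dose, duration and look-back. Leave the cut-off where it is.
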